5.3 Analysis Conventions

This section details the general conventions to be used for data analyses. Departures from these general conventions may be given in the specific detailed sections of this DAP. When this occurs, the rules set forth in the specific section take precedence over the general convention.

- All statistical tests and confidence intervals will use a significance level of $\alpha = 0.05$. Two-tailed tests will be performed for all analyses that use statistical testing. A p-value $\leq \alpha$ will be interpreted as evidence of statistical significance (e.g., 0.024).
- The distribution of continuous variables will be summarized using means, standard deviations (SD) or Standard Errors (SE), medians, minimums, and maximums and the number of patients with non-missing data. Ordinal variables will be summarized using categorical methods if the number of observed response categories is small (usually 4 or fewer) and with medians, minimums and maximums otherwise.
- Summary statistics for discrete variables will consist of the number and percent of responses in each category. All percentages will be rounded to one decimal place. The count and percentage of responses will be presented in the form of XX (XX.X%), where the percentage is in parentheses. If the count is "0" then the percentage may not be presented. If the percentage is "100", the decimal place may be dropped. In addition the decimal place may also be dropped due to space constraints within a table. When reporting proportions or percentages in text, provide the frequencies used to calculate the percentage. For example, "The population included 500 subjects, fifty-two percent (n = 260) of the population was male."
- Use leading zeros for decimal values less than one. For example, use "0.05" rather than ".05".
- Present findings with appropriate indicators of measurement error such as SD, SE or confidence intervals.

CO	NE	IDE	NTI	ΔΙ

- Baseline is defined as the data point collected the closest, but prior to, the date and time when the first treatment of the index procedure is administered unless otherwise specified in this DAP.
- Change from baseline will be calculated by subtracting the Baseline value from the posttreatment Visit value (i.e., Change from baseline = Visit – Baseline).
- If required, for an analysis, partial dates will be completed by imputing the date using the most conservative approach for that specific date.
- All tables will have the population sample size for each treatment group in the column heading.
- All listings will be sorted for presentation in order of site number, subject number, and the
 date-time of the procedure or event, additional listing may be specified in the DAP or mocks

 these listings will be presented per the specifications.

[figure not shown]

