5.2. STATISTICAL METHODOLOGY

This observational study will analyze the outcome measures based on outlined endpoints. The study data will be reported using descriptive analysis.

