17.3. EARLY TERMINATION OF STUDY

The Sponsor may terminate this observational study at any time due to the following reasons, but not limited to: low subject recruitment/enrollment, competing studies and financial reasons. Appropriate notification will be provided to all participating Investigators.

18.DATA ANALYSIS

Study data will be analyzed as indicated in the Data Analysis Plan.

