3.3 Sample Size

Approximately 1,200 subjects will be enrolled in this study. The study cohort will be divided into three study arms according to the most severe clinical syndrome present at the time of study enrollment:

- "Claudicant" Arm (Rutherford 2-3) 500 subjects
- "CLI Rutherford 4-5" Arm 600 subjects
- "CLI Rutherford 6" Arm 100 subjects

The analysis of data for the LIBERTY study will be based on the objectives outlined in the protocol. Analyses will be conducted on locked clinical study data using SAS software (S Institute, Inc., [name]). In the event an analysis is required is better suited for a statistical package other than SAS, this other package (e.g. R) will be used.
For all analyses, Rutherford category will be defined as each study arm. These will be used as
basis for comparisons of treatment and treatment location as well as clinical and economic outc within the study arm. The primary and secondary specific analyses for descriptive purposes and
planned outcome analyses will be performed as pre-specified in this analysis plan.

Baseline patient characteristics and risk factors will be presented by study arm. This will include frequency distributions for categorical variables and summary statistics for continuous variables as

CONFIDENTIAL	
LIBERTY 360 Data Analysis Plan	Page 6

n	17	11	**	2	n	***	O.	te
7			ш	•	.,		7	
•	r	М	-	~	Μ.			•
	•	•		_	٠.		-	

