5.3.2. Analysis Intervals

†

Endpoint analysis on follow-up data may occur at each specified protocol-defined follow-up window (e.g. 30-day, 6-month, 12-month, and annually thereafter) for which it was collected.

CONFIDENTIAL

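### The protocol calls its reporting descriptive, but the SAP attaches a significance verdict at two-sided 0.05 to an unstated number of tests that its visible text neither ranks, adjusts nor labels exploratory

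*SAP*

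**What the plan says.** Protocol 5.2 is short on method: "The study data will be reported using descriptive analysis". Protocol section 18 then hands the detail to the SAP: "Study data will be analyzed as indicated in the Data Analysis Plan".

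SAP 5.3 sets conventions for all analyses. "All statistical tests and confidence intervals will use a significance level of" 0.05, and "Two-tailed tests will be performed for all analyses that use statistical testing". A p-value at or below that level "will be interpreted as evidence of statistical significance". This is a default, since "Departures from these general conventions may be given in the specific detailed sections of this DAP". The two visible endpoint sections (5.1.1 and 5.1.2) plan logistic regressions on covariates or subgroups, without listing the covariates, and do not depart from the default.

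Three other places show how widely the default could apply:

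- The text under SAP 3.3 makes the three Rutherford arms the "basis for comparisons of treatment and treatment location as well as clinical and economic" outcomes within each arm.
- SAP 5.3.2 allows repetition over time: "Endpoint analysis on follow-up data may occur at each specified protocol-defined follow-up window".
- Protocol section 9 schedules visits at 30 days, at 6, 12, 18 and 24 months, and then yearly to 5 years.

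**The concern.** A threshold that turns a p-value into evidence is a decision rule, and it goes further than the description promised in Protocol 5.2. Such a rule needs a statement of which tests it is meant to decide and how error is controlled across them. The visible SAP gives neither, and it does not say that the p-values are exploratory.

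The risk lies in interpretation. Investigators choose the treatment (Protocol 6.2), so contrasts between devices are open to confounding as well as to chance. Protocol 13.2 hopes that the data will help physicians choose care. Under the SAP's present wording, an isolated p of 0.04 for one device or location, in one arm at one visit, could be reported without qualification as statistically significant.

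**Working it through.** The documents give no number of tests, familywise error rate, power or effect size, so there is no figure of the plan's own to reproduce. The check asks how the chance of at least one false positive grows with the number of tests, k, when every null hypothesis is true.

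**Inputs from the documents**

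- Level per test: 0.05, two-sided (SAP 5.3).
- Arms: 3, made up of different patients (SAP 3.3, Protocol 6.1).
- Factors compared within an arm: 2, treatment and treatment location (text under SAP 3.3).
- Acute endpoints: 2, procedural and lesion success (SAP 5.1.1).
- Follow-up windows for major adverse events (MAEs): 30 days and 6, 12, 24, 36, 48 and 60 months make 7. Adding the protocol's 18-month visit, which the examples in SAP 5.3.2 omit, makes 8.

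**Possible counts.** These are constructions from the inputs, not planned numbers. Each contrast is counted as one test.

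- One test per arm: 3.
- Two factors in three arms, one endpoint: 3 × 2 = 6.
- Both success endpoints, no follow-up analysis: 3 × 2 × 2 = 12.
- Success endpoints plus MAEs at every window: 3 × 2 × (2 + 7) = 54, or 3 × 2 × (2 + 8) = 60.

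**Independent tests.** The chance of at least one false positive is 1 − 0.95^k, and the expected number is 0.05 × k.

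| k | Chance of at least one | Expected number |
|---|---|---|
| 3 | 14.3% | 0.15 |
| 6 | 26.5% | 0.3 |
| 12 | 46.0% | 0.6 |
| 54 | 93.7% | 2.7 |
| 60 | 95.4% | 3.0 |

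The k = 3 row is the firmest. The arms share no patients, so with one valid test in each, correlation among other tests within an arm cannot bring the figure below 14.3%.

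**Correlated tests.** Repeated looks at cumulative MAEs are correlated, and so are the two success endpoints. A simulation of 200,000 runs used six independent blocks (3 arms × 2 factors). Its assumptions were:

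- a correlation of 0.7 between the two success endpoints;
- cumulative MAE proportions rising from 5% at 30 days to 55% at 5 years;
- a correlation between two MAE looks equal to the square root of the ratio of their cumulative proportions;
- independence of the success and MAE tests within a block.

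The result was 80.5% for 54 tests and 81.5% for 60, or about 81%.

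With one common correlation across all 54 tests instead, the chance is 82.4% at 0.3, 64.1% at 0.5 and 30.6% at 0.8. That model also correlates tests across arms, which separate patient groups would not be expected to show. All the correlations are assumptions.

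**The case against.** The case on the other side has several good parts.

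- **The protocol is not purely descriptive.** Protocol 5.1 describes a study of outcome predictors, section 8 assesses endpoints by Rutherford class and type of intervention, and section 18 defers to the SAP. A reader might infer a flat contradiction between the documents. They support something milder: deferral lets the SAP add detail but does not withdraw Protocol 5.2, and predictors can be reported as estimates with intervals.
- **The count is not in the plan.** SAP 5.3 covers only analyses that use testing, the endpoint sections speak of estimating and quantifying, and SAP 5.3.2 is permissive. A reader might infer that dozens of tests are planned and that false significant findings are almost certain. The documents do not support that. A 95% chance needs 59 independent tests with every null true. Plausible correlation lowers the chance, and any real effects reduce the number of nulls that can be falsely rejected.
- **The public SAP is incomplete.** It refers to primary and secondary analyses and to a statistical approach described earlier, but little of either can be seen, and no text appears under headings 4, 5.2 or 5.4. A reader might infer that the plan has no error control. That can be said only of the visible text.
- **The remedy leaves the error rate alone.** A 95% interval excludes the null value about as often as p falls below 0.05. This is true, and it is why the remedy concerns interpretation only.

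What remains is the visible rule, its poor fit with Protocol 5.2, and the absence of any visible exploratory label. The rule and the poor fit do not depend on the missing text.

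**Conclusion.** The point holds in limited form. SAP 5.3 attaches a significance verdict to every test performed, in a study whose protocol says the data will be reported descriptively. The visible text does not rank the tests, adjust them or call them exploratory.

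The size cannot be fixed, because the number of tests is unknown. With all nulls true, the illustrations run from 14% (one test per arm) through 46% (12 independent tests) to about 81% (54 to 60 tests under the assumed correlations). All are well above 5%, but none amounts to near certainty. Multiplicity adjustment in an observational registry is debatable, and this point does not ask for it. The matter is a cheap improvement to the wording and does not call for a redesign.

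**What to change.** In SAP 5.3, replace the sentence that interprets p-values with:

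> In line with Protocol 5.2, results are reported as estimates with 95% confidence intervals; unless a specific section pre-specifies a confirmatory test with error control, p-values and intervals are nominal, unadjusted for multiple comparisons and exploratory, and p <= 0.05 will not be taken as confirmatory evidence.

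State in each report the number of comparisons made, so that readers can weigh isolated small p-values.

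The cost is one SAP sentence and one line per report. Every planned analysis and p-value stays, and the word significance is not banned outright. The sponsor gives up unqualified claims of significance for exploratory contrasts. If sections of the SAP that are not visible here already name a confirmatory test with error control, the clause on specific sections preserves it.

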5.3.1. Definition of Baseline Value

For each patient, the last non-missing-valued observation collected prior to first application of treatment will be the baseline value for all subsequent observations. Note that the baseline value may occur on different days for different endpoints but will always fulfill the pretreatment requirement specified above.

5.3.2. Analysis Intervals

†

Endpoint analysis on follow-up data may occur at each specified protocol-defined follow-up window (e.g. 30-day, 6-month, 12-month, and annually thereafter) for which it was collected.

CONFIDENTIAL

5.5 Patient Demographics and Baseline Characteristics

Patient demographics and baseline lesion (s) characteristics will be summarized by study arms.
